9.2.3 Serious Adverse Events Management

Serious adverse events will be attributed as definitely (clearly related to the research), probably (likely related to the research), possibly (may be related to the research), unlikely (doubtfully related to the research) and unrelated (clearly not related to the research).

Treatment related SAEs (TRSAEs) are those attributed as definitely, probably, or possibly related that will be monitored and considered for early stopping of the study according to statistically determined criteria. These include death and any grade IV toxicity considered to be probably or definitely related to study medication. [name] will serve as the independent monitor who reviews the attribution of TRSAEs.

Hospitalizations for administrative issues (to receive a transfusion) or upgrading to ICU for routine monitoring will not be reported as an SAE.

Duration of Serious Adverse Event collecting and reporting: The collection of SAEs will begin on the first day of initiation of the study drug and will continue along as the subject is on study.

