$\geq 1.5g/dL$ above baseline but $\leq 15g/dL$ following at least 2 weeks of-eltrombopag	Keep at current dosage.
>15g/dL (untransfused) at any time on study	Decrease dosage by 50% to lowest dosage that maintains Hb $\geq 1.5g/dL$ above baseline.
>16g/uL (untransfused) at any time on study	Discontinue eltrombopag for one week, if Hb<15g/dL restart at 50% of current dose. Phlebotomy may be performed if clinically indicated as determined by the investigator.

If after 16 to 20 weeks of treatment there is no response, treatment will be discontinued and subjects will go off study per section 8.6.

Dosing for pediatric patients:

Age groups	Daily dose
Non-Asian	
12-18	150 mg
6-11	75 mg
2-5	2.5 mg/kg
East Asian, South East Asian	
12-18	75 mg
6-11	37.5 mg
2-5	1.25 mg/kg

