6.4 Off study assessment

Patients who fail to respond to eltrombopag after 16 or 20 weeks (+/- 10 days) of therapy or who are taken off treatment prior to the 6 months evaluation for any of the other reasons listed in section 8.6 will likely choose to pursue other treatments, including immunosuppressive therapy, related, unrelated donor or cord blood transplantation, or experimental therapies. We will offer patients a follow-up evaluation at the NIH 6 months following being taken off eltrombopag treatment either due to lack of response or for the other reasons listed in section 8.6, but this visit will not be required. If they do not return to the NIH, we will contact their primary hematologist for information on their current hematologic status 6 months following their final dose of eltrombopag, and then take them off study.

If patients do return to the NIH at 6 months (+/- 30 days) for the off study assessment, the following may be performed, and then the patient will be taken off study:

- History and physical examination
- CBC with differential
- Acute care (Na, K, Cl, CO₂, Creatinine, Glucose, and Urea Nitrogen), Mineral (Phosphorus, Magnesium, Albumin, and Calcium), Hepatic (Alk Phosphatase, ALT, AST, Total Bilirubin, and Direct Bilirubin), and Other (Total Protein, CK, Uric Acid, and LDH) panel
- Reticulocyte count
- Peripheral blood smear
- Flow cytometry of the peripheral blood to quantitate GPI-negative cells
- Bone marrow biopsy with reticulin and collagen staining and aspiration with cytogenetics
- Lymphocyte phenotyping (TBNK flow cytometry)
- Research blood as detailed in section 7
- Iron panel (ferritin, transferrin, % saturation) at PI's discretion if indicated for iron metabolism and excretion studies
- 24 hour urine collection to determine the total iron content at PI's discretion if indicated for iron

General Quality of Life FACT questionnaire

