8.6 Off Study Criteria

8.6.1 Per Patient choice: Patients may withdraw from study at their request. The risks of withdrawing will be discussed, as will alternative treatment options. Those subjects who choose to withdraw while taking Eltrombopag will be strongly encouraged to continue to have labs monitored until he/she initiates alternative therapy.

8.6.2 Per principal investigator decision: Should any of the following adverse events occur during the 16 week study period, or in the extension treatment arm in responders, eltrombopag will be discontinued. The subject will be followed until resolution of the event. Labs will be monitored through 30 days off study drug time point or until he/she initiates alternative disease directed therapy at which time the subject's participation on this study will be considered complete and the subject will go off study.

- Intolerance of eltrombopag not resolved by dose reduction
- Life threatening acute hypersensitivity reaction
- Thrombosis/embolism (DVT, PE, stroke or TIA, myocardial infarction) other than central line thrombosis
- Persistent hepatotoxicity as defined in section 5.3.2
- New or worsening morphological abnormalities or cytopenia(s) as defined in section 5.4.2

- No treatment response after 16 to 20 weeks of treatment
- Any Grade IV toxicity considered related to the study medication excluding readily reversible metabolic or laboratory abnormalities or hematologic toxicities
- Significant progression of disease or a concomitant condition that would make the subject ineligible for further protocol participation
- Pregnancy or unwillingness to use acceptable forms of contraception
- Initiation of non-protocol therapy for aplastic anemia or bone marrow failure and unilineage cytopenia
- Cytogenetic abnormalities, new or worsening morphological abnormalities or cytopenia(s) as defined in section 5.4.2.
- Non-compliance with protocol procedures
- Lost to follow-up
- Study Completion

Once off study (either by per patient choice or per PI decision), subjects will be referred back to his or her referring physician or consented to the Hematology Branch evaluation and treatment protocol (94-H-0010) for consideration for standard therapy or evaluation for eligibility for another Branch protocol, depending on what is considered to be in the best interest of the subject.

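### SAE collection ends when a subject goes off study, and section 8.6.2 can put that before day 30 for a subject whom section 6.4 and Appendix B keep on study to about month 6

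*Combined protocol and SAP*

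**What the plan says.** - **Section 9.2.3** starts SAE collection at first dose and says it "will continue along as the subject is on study". It names no number of days after the last dose.
- **Section 8.6.2** lists the reasons for stopping drug, including no response after 16 to 20 weeks, unresolved intolerance, thrombosis, and "Initiation of non-protocol therapy for aplastic anemia or bone marrow failure and unilineage cytopenia". The subject is followed until the triggering event resolves. Then: "Labs will be monitored through 30 days off study drug time point or until he/she initiates alternative disease directed therapy", at which point "participation on this study will be considered complete and the subject will go off study".
- **Section 5.2** sends non-responders to that rule: "treatment will be discontinued and subjects will go off study per section 8.6". Sections 3.0 and 5.4.1 also send subjects off study but give no interval, so they are best read as deferring to 8.6.
- **Section 6.4** covers non-responders and also those stopped early "for any of the other reasons listed in section 8.6 will likely choose to pursue other treatments". It offers an optional visit at 6 months; otherwise staff contact the hematologist "for information on their current hematologic status 6 months following their final dose of eltrombopag, and then take them off study".
- **Appendix B** (initial treatment phase) carries an optional month-6 off-study column and no day-30 column.
- **Day 30 elsewhere.** Section 9.2.2 limits AE reporting to related events from 30 days after the last dose. Section 9.2.4.6 has unexpected related SAEs reported to the CRADA partner if they occur during the study or within 30 days of the last dose.
- **Section 8.6.1:** "Patients may withdraw from study at their request".

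**The concern.** Because 9.2.3 ties collection to on-study status, the off-study date decides which SAEs enter the data. Under 8.6.2 that date can be the day another therapy starts, and 6.4 expects these patients to seek other therapy. Under 6.4 the same patient stays in SAE collection for about 6 months. Nothing in the plan says which rule governs.

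What is at stake is whether post-treatment safety data are complete and consistent. Toxicity is part of the primary endpoint (section 8.2). Two outputs call for all SAEs, not only related ones: the report to the Clinical Director (9.2.4.1) and the annual summary to the sponsor and FDA (9.2.4.5). Relatedness can be judged only for an event that has been collected. An exit date set by the next therapy can therefore remove events before anyone attributes them.

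**Working it through.** The plan states no figure for this window, so there is none to reproduce. The check compares the sections and then counts the subjects who fall under both rules.

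**1. End of SAE collection for the same non-responder, counted from the last dose**
- Under 8.6.2: from about day 0, if other therapy starts at once, up to day 30. The text sets no minimum and does not say whichever is later.
- Under 6.4 and Appendix B: about month 6, or roughly day 183.
- The latest 8.6.2 exit and the 6.4 exit differ by 183 - 30 = 153 days.

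**2. Part of the 30-day window that 8.6.2 can remove**

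If other therapy starts on day d off drug, the loss is 30 - d days. The documents do not give d, so these values are illustrative:
- d = 1: 29 days (97%)
- d = 7: 23 days (77%)
- d = 14: 16 days (53%)
- d = 21: 9 days (30%)

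**3. Expected non-responders under both rules**

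Inputs from section 8.3: 18 subjects at stage 1, stop if 4 or fewer respond, otherwise 15 more. The null response rate is 20% and the alternative 40%.

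Expected enrolment = 18 + 15 × [1 - P(X ≤ 4)], with X binomial(18, p). Expected non-responders = (1 - p) × expected enrolment.
- p = 0.20: P(X ≤ 4) = 0.716. Enrolment = 18 + 15 × 0.284 = 22.3. Non-responders = 0.80 × 22.3 = 17.8.
- p = 0.40: P(X ≤ 4) = 0.094. Enrolment = 18 + 15 × 0.906 = 31.6. Non-responders = 0.60 × 31.6 = 19.0.

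If all 33 are enrolled, the figures are 33 × 0.80 = 26.4 and 33 × 0.60 = 19.8. Early stoppers are additional. These are subjects covered by the conflict, not missed SAEs.

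**4. Drug still present at exit**

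Section 2.4.5 gives a half-life of 26 to 35 hours in ITP. Assuming it holds in MAA, five half-lives are 5 × 26 = 130 h (5.4 days) to 5 × 35 = 175 h (7.3 days). Exit in the first week could end collection with drug still in plasma. Later exits would mainly lose expected or unrelated events.

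**5. What is not touched**

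The section 8.3 test counts responders by week 16 to 20. The section 8.5 boundary counts events in the treatment period. Neither uses SAEs arising after the drug is stopped. Responders followed off drug under 6.3.1 have their own 3-year schedule and are outside the conflict.

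**The case against.** The strongest reply is that 8.6.2 is the outlier. The 6-month exit stands both in 6.4 and in the schedule of events. If staff follow those, 9.2.3 already collects all SAEs to about month 6, well past day 30, and the early gap never arises. This stands: the problem is a drafting conflict, with a loss only if 8.6.2 prevails. But 5.2 points non-responders to section 8.6, so 8.6.2 cannot be set aside as stray text.

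The second reply is that the most important events have other cover:
- 9.2.4.6 reaches unexpected related SAEs within 30 days of the last dose, even in a subject already off study.
- 9.2.2 counts its 30 days from the last dose and keeps related events reportable afterwards.
- 9.2.4.1 requires SAEs and deaths to be reported from when the investigator learns of them, with no on-study condition.
- 8.6.2 follows the triggering event to resolution.

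This also stands in large part. What remains is new SAEs before day 30, mainly expected or unrelated, in subjects already on another therapy, where attribution is harder. These provisions are partly passive, however. They govern reporting and do not set an active collection period.

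Third, section 8.2 states no post-treatment window for the toxicity profile, so damage to the primary endpoint is not shown. That is fair. The clearer claim concerns the outputs that need all SAEs.

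A reader might infer that the plan stops all safety follow-up when the next therapy starts, that related SAEs are generally lost, or that the safety stopping rule is weakened. The sections above do not support any of these.

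**Conclusion.** The concern holds in a limited form. Sections 8.6.2 and 6.4 give one subject two off-study dates, and 9.2.3 lets that date end SAE collection. If 8.6.2 is followed, collection can stop before the day-30 mark that 9.2.2 and 9.2.4.6 use. From day 30 to about month 6, whether an SAE is collected depends on which section staff apply.

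Allowing for the stage-1 stop, about 18 or 19 expected non-responders fall under both rules, at response rates of 20% and 40%; early stoppers add to this. A reader might take 26 of 33 as the figure under the null, but that requires full enrolment despite the stage-1 rule. The number of missed SAEs cannot be estimated, because the documents give neither the start date of the next therapy nor a post-treatment SAE rate. This is an inexpensive improvement to safety data, not a threat to the efficacy conclusion or the stopping boundary.

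**What to change.** 1. **Section 9.2.3:** collect all SAEs from first dose through the later of 30 days after the last dose and the off-study date, regardless of new therapy, unless the subject withdraws consent to data collection. Do not restrict collection to related events after day 30. Under 6.4 that would shrink what 9.2.3 now collects.
2. **Section 8.6.2:** rename the trigger as off treatment. State that starting alternative therapy may end lab monitoring but does not end SAE collection. Make the 6-month contact in 6.4 and Appendix B the single off-study point.
3. **Section 6.4:** have that planned contact ask about SAEs and the start date of the next therapy, as well as hematologic status. A day-30 phone call is optional, since none is now scheduled.

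The cost is a short text change in three sections and a few extra questions at a contact already planned; the optional call would add a little staff time. Sample size, endpoint and dosing do not change. The downside is that some added events will be confounded by the next therapy. Recording its start date helps only in part.

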9.2.4.1 Reporting Timeframes to IRB Chair, Clinical Director, and/or IRB

Serious Events

Reports to the IRB and CD: The PI must report Serious UPs, and Serious PDs to the IRB and CD as soon as possible but not more than 7 days after the PI first learns of the event using the IRB system or other approved formats.

Reports to the CD: The PI must report all SAEs that do not meet the definition of UP to the CD not more than 14 days after the PI first learns of the event using via email.

Non-serious Events

Reports to the IRB and CD: The PI must report all UPs that are not Serious to the IRB and CD, and PDs that are not Serious to the IRB, not more than 14 days after the PI first learns of the event using the IRB system or other approved formats.

Deaths

The PI must report all deaths (that are not UPs) to the CD as soon as possible, but not more than 7 days after the PI first learns of the event.

9.2.4.2 At continuing review, the PI will provide to the IRB a summary of:

- All UPs
- All PDs
- All AEs (except for those granted a waiver of reporting)
- If, while preparing the continuing review, the PI identifies a greater frequency or level of severity of expected adverse events than was previously identified in the protocol or investigational brochure (IB), these should be reported separately as a UP. If such an observation occurs before the time of continuing IRB review, it should be reported to the IRB and CD as a UP in the time frames noted above, and summarized at the time of continuing review.

Exclusions to data reporting:

The following Adverse Events will be captured only in the source documents and will not be reported to the IRB at the time of continuing review.

- Laboratory values that do not meet the definition of AE listed in Section 9.2.2.
- All grade 1 events listed as expected in the investigator's brochure, package insert, and/or anticipated events.

9.2.4.4 NHLBI DSMB:

All grade 4 TRSAEs and reports of serious adverse events that are unexpected and thought to be related to the experimental drug will also be forwarded immediately to the Data and Safety Monitoring Board (DSMB). A summary of events will be included in DSMB reports for review by the DSMB.

9.2.4.5 Sponsor and FDA Reporting

IND #: 104,877

Sponsor Representative: [name]., TSCBB, NHLBI

The PI will report SAEs to the Sponsor according to the requirements of 21 CFR 312.64(b) and as agreed upon with the sponsor. The Sponsor (or designee) will determine the reportability of the event to the FDA and IND safety report will be submitted to the FDA as required. The PI or designee will report SAEs to the Sponsor within 24 to 72 hours of discover.

IND Annual Report

A summary of all SAEs, non-serious AEs, and other events will be recorded and submitted to the Sponsor and FDA in annual progress reports (21 CFR 312.64(b)). Annual progress reports will be submitted within 60 days after the anniversary date of the IND.

IND Safety Reports to the FDA (Refer to 21 CFR 312.32)

The sponsor must notify FDA in an IND safety report of potential serious risks, from clinical trials or any other source, as soon as possible, but in no case later than 15 calendar days after the sponsor determines that the information qualifies for reporting. The sponsor must also notify FDA of any unexpected fatal or life-threatening suspected adverse reaction as soon as possible but in no case later than 7 calendar days after the sponsor's initial receipt of the information.

15-day reporting

The sponsor must report any suspected adverse reaction that is both serious and unexpected. The sponsor must report an adverse event as a suspected adverse reaction only if there is evidence to suggest a causal relationship between the drug and the adverse event, such as:

- A single occurrence of an event that is uncommon and known to be strongly associated with drug exposure (e.g., angioedema, hepatic injury, Stevens-Johnson Syndrome);
- One or more occurrences of an event that is not commonly associated with drug exposure, but is otherwise uncommon in the population exposed to the drug (e.g., tendon rupture);
- An aggregate analysis of specific events observed in a clinical trial (such as known consequences of the underlying disease or condition under investigation or other events that commonly occur in the study population independent of drug therapy) that indicates those events occur more frequently in the drug treatment group than in a concurrent or historical control group

The sponsor must submit each IND safety report in a narrative format or on FDA Form 3500A.

FDA contact: [name], M.A.
Regulatory Project Manager, Food and Drug Administration
Food & Drug Administration Document Room
Center for Drug Evaluation and Research
Division of Hematology Products
[name]
[name]
[contact] (phone)

9.2.4.6 Reporting Serious Adverse Events to CRADA Sponsor Novartis:

All unexpected and possibly, probably or definitely related SAEs occurring during the study or within 30 days of the last administration of eltrombopag will be reported to Novartis within 24 hours of the research team learning of the event. A copy of the SAE report will be forwarded as soon as possible, but no later than seven (7) days in the case of death or life-threatening serious adverse events or within fifteen (15) days after the occurrence of all other forms of serious adverse events. If the SAE is unexpected and determined possibly, probably or definitely related to study drug the SAE report will be forwarded to Novartis and FDA within 24 hours of learning of event. Follow-up reports regarding the patient's subsequent course will be submitted until the SAE has resolved or until the patient's condition stabilizes (in the case of persistent impairment) or the patient dies. The SAE report will contain a full written summary detailing relevant aspects of the adverse events in question. Where applicable, information from relevant hospital case records and autopsy reports will be included. The investigator will always provide an assessment of causality at the time of the initial report as described in 'Assessment of

Causality’.

Novartis Contact: [name]
Clinical Research Manager
Novartis Pharmaceuticals Corporation
[name]
[name]
USA
[contact]
[contact]
[contact]
[contact]

9.3 Reporting of pregnancy

Subjects who become pregnant during the study should discontinue the study immediately. The investigator, or his/her designee, will collect pregnancy information on any subject who becomes pregnant while participating in this study. The investigator, or his/her designee, will submit pregnancy information to Novartis within two weeks of learning of a subject’s pregnancy. Information on the status of the mother and child will be forwarded to Novartis. Generally, follow-up will be no longer than 6 to 8 weeks following the estimated delivery date. Any premature termination of the pregnancy will be reported.

While pregnancy itself is not considered to be an AE or SAE, any pregnancy complication or elective termination of a pregnancy for medical reasons will be recorded and reported to Novartis as an AE or SAE. A spontaneous abortion is always considered to be an SAE and will be reported to Novartis. Furthermore, any SAE occurring as a result of a post-study pregnancy and is considered reasonably related to the investigational product by the investigator, will be reported to Novartis. While the investigator is not obligated to actively seek this information in former study participants, he/she may learn of an SAE through spontaneous reporting.

9.4 Data management

Data collection and distribution:

The PI will be responsible for overseeing entry of data into an in-house password protected electronic system and ensuring data accuracy, consistency and timeliness. The principal investigator, associate investigators/research nurses and/or a contracted data manager will assist with the data management efforts. All human subjects personally identifiable information (PII) as defined in accordance to the Health Insurance Portability and Accountability, eligibility and consent verification will be recorded. Primary data obtained during the conduct of the protocol will be kept in secure network drives or in approved alternative sites that comply with NIH security standards. Primary and final analyzed data will have identifiers so that research data can be attributed to an individual human subject participant or other unique code, or minimum PII required for subject identification.

Novartis will receive-quarterly accrual and toxicity information as detailed in the CRADA. In order to maintain patient confidentiality, all communications relating to the study will identify participants by assigned subject study numbers. No personally identifiable information will be sent to Novartis. In accordance with local and federal regulations, the Investigator will allow Novartis personnel or their designee, access to all pertinent medical records in order to verify the data gathered and to audit the data collection process.

The US Food and Drug Administration (FDA) may also request access to all study records, including source documentation for inspection

End of study procedures: Data will be stored in locked cabinets and in a password protected database until it is no longer of scientific value.

Loss or destruction of data: Should we become aware that a major breach in our plan to protect patient confidentiality and trial data has occurred, the IRB will be notified.

Publication Policy: Given the research mandate of the NIH, patient data including the results of testing and responses to treatment will be entered into an NIH-authorized and controlled research database. Any future research use will occur only after appropriate human subject protection institutional approval such as prospective NIH IRB review and approval or an exemption from the NIH Office of Human Subjects Research Protections (OHSRP).

